The PUCAI score will be assessed using subject-reported symptoms and activity level. The answers should reflect symptoms and activity level during the previous 24 hours. The PUCAI scores of the last 2 days prior to each study visit will be averaged and used for the PUCAI scores for each study visit. The total PUCAI score will be rounded up to the next 5-point interval as applicable. In order to account for unavailable or excluded diary entries as per the provisions given below diary entries for the PUCAI score of the most recent 2 days within 10 days prior to each study visit will be used.

Diary entries of the following days should not be included in the 2 days prior to the visit that are evaluated for the PUCAI score: (1) the day the subject received medication for bowel preparation prior to endoscopy, (2) the day the subject underwent an endoscopy, and (3) 2 days following the endoscopy. Earlier diary entries will be used accordingly in order to provide the most recent data for 2 days prior to the respective study visit.

The subscore for the number of stools per 24 hours during days which a subject received anti-diarrheal medication will be scored as 15.

Mayo Score

All subjects will be provided with a Subject Diary at the Baseline Visit where they will record ulcerative colitis related symptoms. The Partial Mayo Score will be calculated from the subject diary at each visit beginning at Baseline. The average entry from the 5 days prior to each study visit will be used for each subject-reported subscore. In addition to the physical examination, the investigator should use the subject-reported

subscores of abdominal discomfort and functional assessment to determine the physician's global assessment subscore.

Normal number of bowel movement is the number of stools per day (24 hours) that is typical for the subject when having active UC but not experiencing a flare. Each subject serves as his or her own control to establish the degree of abnormality of the stool frequency.

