Subjects will record the daily number of stools throughout the trial. Using these numbers, the Stool Frequency subscore will be assessed for each study day as follows:

- A number of bowel movements lower than or equal to the normal number of bowel movements should be scored as 0 = Normal.
- One or 2 bowel movements more than the normal number of bowel movements should be scored as 1.
- Three or 4 bowel movements more than the normal number of bowel movements should be scored as 2.
- Five or more bowel movements more than the normal number of bowel movements should be scored as 3.

The Stool Frequency subscores from the 5 days prior to each study visit will be averaged and used for the Stool Frequency subscore for each study visit. In order to account for unavailable or excluded diary entries as per the provisions given below diary entries of the most recent 5 days within 14 days prior to each study visit will be used.

The Stool Frequency subscore during days which the subject received anti-diarrheal medication will be scored as a 3. Diary entries for stool frequency should not be included in the 5 days prior to the visit that are evaluated for the Stool Frequency subscore for the following days: (1) the day the subject received medication for bowel preparation prior to endoscopy, (2) the day the subject underwent an endoscopy, and (3) 2 days following the endoscopy. Earlier diary entries will be used accordingly in order to provide the most recent data for 5 days prior to the respective study visit.

[figure not shown]
Rectal Bleeding Subscore

Subjects should record a daily rectal bleeding subscore value as follows:

- No visible blood with stool during the respective day should be scored as 0.
- Visible blood with stool less than half the time during the respective day should be scored as 1.
- Visible blood with stool at least half the time during the respective day should be scored as 2.
- A score of 3 for bleeding requires subjects to have at least 50% of bowel motions accompanied by visible blood and at least one bowel motion with blood alone.

The score entries into subject's diary from the 5 days prior to each study visit will be averaged and used for the Rectal Bleeding subscore for each study visit. In order to account for unavailable or excluded diary entries as per the provisions given below diary entries of the most recent 5 days within 14 days prior to each study visit will be used.

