For composite scores which consist of several component subscores, components will be imputed first and the composite score will be calculated based on imputed component subscores. Only if composite score still can't be calculated after imputing component subscores, then the previous composite score will be carried forward.

[figure not shown]

Missing Items on Questionnaire Scales:

Mayo scores (and alternative composite scores) can only be calculated if all subscores included are collected. If one or more subscores are missing, the score will be considered missing. No imputations will be made. The symptoms of stool frequency and rectal bleeding are scored as a 5 day average of daily values from up to 14 days preceding the visit, rounded to one decimal place. The most recent consecutive days will be used. If consecutive days are not available, then non-consecutive days can be used. Diary entries for stool frequency and rectal bleeding should not be included in the 5 days prior to the visit that are evaluated for these subscores for the following days: (1) the day the subject received medication for bowel preparation prior to endoscopy, (2) the day the subject underwent an endoscopy, and (3) 2 days following the endoscopy. Earlier diary entries will be used accordingly in order to provide the most recent data for 5 days prior to the respective study visit. If less than 3 days of diary data are available, stool frequency and rectal bleeding subscores will be considered missing.

[figure not shown]
When calculating **PUCAI**, if more than 3 subscores are missing then PUCAI will be considered missing. Otherwise, for missing subscores, the last available post-baseline value for the respective subscore will be carried forward to compute the total PUCAI score. The subscores of abdominal pain, rectal bleeding, stool consistency, number of stools per 24 hours, nocturnal stools and activity level are scored as a 2 day average, rounded to one decimal place. The most recent consecutive days will be used. If consecutive days are not available, then non-consecutive days can be used.

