2. PUCAI

Pediatric Ulcerative Colitis Activity Index (PUCAI) is calculated as the sum of six subscores [each being a 2 day average, see above] of PUCAI (abdominal pain [no pain = 0, pain can be ignored = 5, pain cannot be ignored = 10], rectal bleeding [none = 0, small amount with < 50% of stools = 10, small amount with most stools = 20, large amount with > 50% of stool content = 30], stool consistency of most stools [formed = 0, partially formed = 5, completely unformed = 10], number of stools per 24 hours [0 to 2 = 0, 3 to 5 = 5, 6 to 8 = 10, > 8 = 15], nocturnal stools [no = 0, yes = 10], activity level [no limitation = 0, occasionally limited = 5, severe restriction = 10]) with maximum total score 85. Higher scores represent more severe disease.

- PUCAI remission is defined as PUCAI < 10.
- PUCAI response is defined as a decrease in PUCAI ≥ 20 points from Study M11-290-Baseline.

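### The SAP's PUCAI derivation omits two protocol scoring rules (stool item 15 on anti-diarrheal days, round-up to the next 5 points), so a child not in remission under the protocol can be counted in PUCAI remission

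*SAP*

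**What the plan says.** **Protocol, PUCAI.** Section 5.3.1.1 (Study Procedures, PUCAI) averages the last two eligible diary days and adds two rules. First, "The subscore for the number of stools per 24 hours during days which a subject received anti-diarrheal medication will be scored as 15". Second, "The total PUCAI score will be rounded up to the next 5-point interval as applicable".

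**Protocol, Mayo.** Appendix D has the parallel rule: "The Stool Frequency subscore during days which the subject received anti-diarrheal medication will be scored as a 3". The value 3 is the top of that subscore, as 15 is the top of the PUCAI stool item.

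**SAP, PUCAI.** Section 6.0 (Missing Items on Questionnaire Scales) says that "number of stools per 24 hours, nocturnal stools and activity level are scored as a 2 day average", with each item rounded to one decimal. The PUCAI entry under Score Definitions gives the points by count alone: "number of stools per 24 hours [0 to 2 = 0, 3 to 5 = 5, 6 to 8 = 10", and 15 for more than 8 stools. Neither place mentions anti-diarrheals or a round-up of the total. The general Rounding paragraph in 6.0 confines rounding to presentation, so the round-up cannot be read in by default.

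**SAP, Mayo.** The same section says: "The symptoms of stool frequency and rectal bleeding are scored as a 5 day average of daily values", looking back no more than 14 days. It then repeats Appendix D's exclusion of days around an endoscopy, but not the anti-diarrheal sentence that stands just before that exclusion in Appendix D.

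The SAP's only mention of anti-diarrheals is in 7.3, as a class of therapy taken before Study M11-290. Protocol 5.2.3.3 does not list them among the prohibited drugs.

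**The concern.** An anti-diarrheal lowers the stool count whatever the state of the colitis. The protocol deals with this by giving the stool item its worst value on days of use. The SAP is the document the programmers work from, and its PUCAI derivation is complete enough to be coded without opening the protocol. Coded that way, a drug-suppressed count is scored as reported. For remission the error runs in one direction: leaving out either rule can lower a post-baseline PUCAI but never raise it. The study has no control arm in which such an effect would show, and Protocol 8.1.7 intends the interim results for regulatory submission.

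The Mayo omission raises the same worry for PMS and for the full, 9-point and 6-point Mayo endpoints, but it depends on where those scores come from.

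**Working it through.** **Inputs.** PUCAI item maxima 10, 30, 10, 15, 10, 10 (Protocol Appendix C; SAP Score Definitions). PUCAI remission is a score below 10. The Mayo stool subscore runs from 0 to 3 and is averaged over 5 days; it is set to missing under this condition: "If less than 3 days of diary data are available". Expected main-study size is 55 (SAP 4.3).

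**The plan's own figure.** 10 + 30 + 10 + 15 + 10 + 10 = 85, the stated PUCAI maximum. It is reproduced.

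**PUCAI.** Take a child whose suppressed count scores 0 and whose other items are all 0. With anti-diarrheal use on d of the 2 days, the override gives 15d/2, and the round-up takes this to the next multiple of 5.

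| Days of use | SAP as written | Override only | Override and round-up (protocol) |
|---|---|---|---|
| 0 | 0, remission | 0, remission | 0, remission |
| 1 | 0, remission | 7.5, remission | 10, not remission |
| 2 | 0, remission | 15, not remission | 15, not remission |

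Use on both days changes the classification through the override alone. Use on one day changes it only when both rules are restored; the round-up alone would leave that child at 0.

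The round-up also matters without any anti-diarrheal. Daily totals are multiples of 5, so two-day averages are multiples of 2.5. A total of 7.5 is therefore remission under the SAP and becomes 10, not remission, under the protocol.

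**Mayo, only if subscores are re-derived from raw counts.** With use on k of 5 days and everything else 0, the stool subscore is 3k/5:

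- k = 1: 0.6
- k = 2: 1.2
- k = 3: 1.8
- k = 4: 2.4
- k = 5: 3.0

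Without the rule it is 0 for every k. From k = 2 the child fails PMS remission, and also fails 6-point remission (at most 1). The PMS result is the same whether the subscore condition is read as none above 1 (protocol synopsis) or none at 1 or above (Protocol 5.3.2, SAP Table 2). At k = 1 nothing changes. With only 3 diary days, k = 1 gives 3/3 = 1.0, and the two printed conditions then disagree.

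At k = 5 the PMS is 3 against 0. With a Baseline PMS of 0, the protocol score would meet the disease-flare criterion of at least 3 points above Baseline, at a visit the analysis would count as remission.

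**Size per child.** 1/55 = 1.8 percentage points at a visit where all 55 are analysed. The documents do not say how often anti-diarrheals are used, so the total effect cannot be computed.

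**The case against.** The SAP sets out to elaborate the protocol and nowhere revokes the scoring rules; its averaging text sits under a heading about missing items. That is fair, but silence is not enough for PUCAI. The SAP gives the PUCAI points by stool count, the averaging, the rounding of items and the sum, so following it exactly yields a score that the protocol contradicts.

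For Mayo the objection largely stands. A reader might infer that the SAP replaces Mayo scoring too, and that PMS and Mayo remission must be misclassified. The documents do not support this. The SAP never says how a stool count becomes 0, 1, 2 or 3; that step is only in Appendix D, in the same section as the anti-diarrheal rule. Protocol 5.3.1.1 also has the visit-level stool subscore, PMS and Mayo score entered in the eCRF. If the analysis uses those values, or daily values already scored under Appendix D, Mayo is protected. The SAP does not say which source it uses.

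A reader might also infer that every efficacy endpoint is tilted towards adalimumab. This is not established for response, which is measured against Study M11-290 Baseline. If those scores also lacked the override, Baseline would be lower and response harder to reach. The documents do not show how they were scored.

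Three further limits stand. Anti-diarrheals are merely not prohibited; no text expressly allows them. The examples assume that every other item is 0. Efficacy is descriptive, with no confirmatory test at stake.

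**Conclusion.** The point holds for PUCAI. The SAP omits two protocol scoring rules, and together they decide remission for an otherwise symptom-free child who used an anti-diarrheal on either scoring day. For Mayo and PMS the omission is real, but its effect is conditional on the data source.

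This rests on PUCAI being programmed from the SAP text, with item scores that do not already contain the override. No document says that they do: Protocol 10.3 gives examples of diary items, without anti-diarrheal use among them, and there is no PUCAI counterpart to the eCRF entry of Mayo averages. The SAP cites protocol Amendment 3 and the protocol reviewed is Amendment 5. Amendment 5's summary of changes lists no scoring change and Amendment 4's is not available, but the SAP and the current protocol differ either way.

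The size is about 1.8 percentage points per reclassified child, with an unknown number of children. The one-way bias is established for remission only. Severity is moderate: a correction to make before programming is final, not a threat to the study's safety conclusions.

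**What to change.** In SAP 6.0:

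1. Before averaging, set the daily PUCAI stool item to 15 and the daily Mayo stool frequency subscore to 3 on each diary day with recorded anti-diarrheal use.
2. Round the PUCAI total up to the next multiple of 5, as a named exception to the Rounding paragraph. Without this step, use on one of the two days still gives 7.5 and remission.
3. Identify use from the M10-870 concomitant-medication records. The grouping in SAP 7.3 will not serve, because it covers therapy before Study M11-290. State a convention for date ranges and intermittent use, since applying a whole range could override days on which no dose was taken.
4. State whether Mayo and PMS are taken from eCRF values that already include the rule. If they are re-derived, check them against those values.

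The cost is some SAP wording and a little programming on data already collected, with imprecision where only date ranges exist. Remission rates may come out slightly lower.

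### The SAP picks PUCAI diary days by a different rule from the protocol (no bowel-preparation or endoscopy exclusion, no 10-day limit, consecutive days first); for Mayo only the consecutive-days preference differs

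*SAP*

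**What the plan says.** **PUCAI, protocol.** Section 5.3.1.1 averages the last two days before the visit. To allow for unavailable or excluded entries, "diary entries for the PUCAI score of the most recent 2 days within 10 days prior to each study visit will be used". It then lists three kinds of day to leave out: "Diary entries of the following days should not be included in the 2 days prior to the visit that are evaluated for the PUCAI score". These are the bowel-preparation day, the endoscopy day and the two days after endoscopy. There is no condition that the two days be adjacent. The section also scores the stool-number item as 15 on anti-diarrheal days and rounds the total up to the next 5-point step.

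**PUCAI, SAP.** Section 6.0 (Missing Items on Questionnaire Scales) says the subscores are "scored as a 2 day average, rounded to one decimal place. The most recent consecutive days will be used". The fallback is: "If consecutive days are not available, then non-consecutive days can be used". No excluded days, look-back limit, anti-diarrheal rule or 5-point rounding is given. The PUCAI score definition later in the section only refers back to this rule.

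**Mayo, protocol.** In Appendix D, for stool frequency and rectal bleeding, "diary entries of the most recent 5 days within 14 days prior to each study visit will be used", with the same three exclusions. Stool frequency is scored 3 on anti-diarrheal days.

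**Mayo, SAP.** Section 6.0 repeats the 14-day limit and all three exclusions. It adds the same preference for consecutive days and leaves out the anti-diarrheal score.

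**The concern.** The SAP says it exists to guide statistical programming. In adjacent paragraphs it writes out the exclusions and the look-back limit for Mayo, then gives PUCAI a complete-looking rule with neither. A programmer could reasonably conclude that they do not apply to PUCAI.

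PUCAI remission and PUCAI response are two of the four efficacy endpoints listed in protocol section 5.3.2. Symptoms caused by bowel preparation push the score up for a reason unrelated to disease activity, and they cluster around endoscopy.

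The consecutive-days preference is a separate matter. It is a different instruction, not an omission, and it applies to both scores. Sites record averaged Mayo subscores and the partial Mayo score in the eCRF (protocol 5.3.1.1), so a value derived under the SAP rule could disagree with the recorded one for the same visit.

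**Working it through.** The plan gives no figure to reproduce here, so the check applies both rules to the same diaries. Days are counted back from the visit (Day 1 is the day before). The SAP is read literally: the most recent run of consecutive days, otherwise non-consecutive days.

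**1. PUCAI near an endoscopy.** Assumptions: a full diary and preparation on the day before endoscopy. With endoscopy *e* days before the visit, the protocol excludes Days *e*+1, *e*, *e*−1 and *e*−2.

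| Endoscopy, days before visit | Protocol uses | SAP uses | Excluded days scored by SAP |
|---|---|---|---|
| 0 | 2, 3 | 1, 2 | Day 1 (preparation) |
| 1 | 3, 4 | 1, 2 | Day 2 (preparation), Day 1 (endoscopy) |
| 2 | 4, 5 | 1, 2 | Day 2 (endoscopy), Day 1 (day after) |
| 3 | 5, 6 | 1, 2 | Days 2 and 1 (days after) |
| 4 | 1, 6 | 1, 2 | Day 2 (second day after) |
| 5 | 1, 2 | 1, 2 | none |

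The preparation day itself enters only at 0 or 1 days.

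**2. Effect on remission (PUCAI < 10).** Item points are from protocol Appendix C; the day patterns are illustrative. Each preparation day is averaged with a symptom-free day:

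- Unformed stool 10 + 3–5 stools 5 = 15; (15 + 0)/2 = 7.5, still below 10 under the SAP's calculation.
- Unformed 10 + 6–8 stools 10 = 20; (20 + 0)/2 = 10, not remission.
- Unformed 10 + more than 8 stools 15 + nocturnal 10 = 35; (35 + 0)/2 = 17.5, not remission.

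The threshold is therefore a preparation-day score of 20. For response (a fall of at least 20 points from Study M11-290 Baseline), the 20-point day removes 10 points from the apparent fall.

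**3. Look-back limit.** With entries on Days 12 and 13 only, the protocol has no usable PUCAI entry, while the SAP rule yields a score.

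**4. Consecutive days first.**

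- PUCAI, Day 2 missing: the protocol uses Days 1 and 3; the SAP uses Days 3 and 4.
- Mayo, Day 2 missing: the protocol uses Days 1, 3, 4, 5, 6; the SAP uses Days 3 to 7. Four of the five days are shared.

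All 2^14 patterns of present and absent entries were enumerated, with an assumed independent daily completion probability *p* and no endoscopy. Share of visits at which the rules choose different days:

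| Assumed *p* | PUCAI | Mayo |
|---|---|---|
| 0.70 | 30% | 33% |
| 0.80 | 20% | 40% |
| 0.90 | 10% | 31% |
| 0.95 | 5% | 18% |

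A hand check agrees. For PUCAI the rules differ essentially when the day before the most recent entry is missing, so the share is about 1 − *p*. For Mayo the ceiling is 1 − *p*^4 (0.19 at *p* = 0.95, 0.34 at 0.90). The enumerated share is lower because sometimes no run of five exists within 14 days, and the rules then agree. Different days need not mean a different score.

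**5. Rounding.** With Day 2 missing and illustrative daily PUCAI scores of 10, 5 and 5 on Days 1, 3 and 4, the protocol mean is (10 + 5)/2 = 7.5, rounded up to 10: not remission. The SAP mean is (5 + 5)/2 = 5: remission. Without the round-up both are below 10, so this reversal needs the rounding difference as well as the day difference.

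**6. Weight of one subject.** With about 55 subjects outside Japan (SAP 4.3), one misclassified subject moves a full-set proportion by 1/55 = 1.8 percentage points.

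**The case against.** The strongest reply is that the SAP only elaborates the protocol, so its silence on PUCAI exclusions leaves the protocol rule in force. Nothing in the SAP tells anyone to include preparation days. That is fair as far as it goes: for exclusions and look-back the SAP omits, it does not give the opposite instruction, and a careful programmer could apply the protocol. It does not settle the matter, because the SAP spells out the same provisions for Mayo in the adjacent paragraph. Nor does it reach the consecutive-days preference, which is a positive instruction at odds with the protocol.

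Two stronger readings are tempting, and the documents do not support them.

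- A reader might infer that PUCAI is wrong at every endoscopy visit (Weeks 48, 96, 192 and 288/Premature Discontinuation), making subjects in remission look active. Endoscopy is optional at those visits, the windows differ only for endoscopies close to the visit, and a status change needs a high enough score. The documents say nothing about preparation-day symptoms and allow sigmoidoscopy as well as colonoscopy.
- A reader might infer that the Mayo rule has the same gap. It does not: its 14-day limit and exclusions match the protocol. No change of Mayo or partial Mayo status has been shown. The SAP's own phrase about providing the most recent five days of data allows a softer reading of the consecutive-days sentence.

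On versions, the SAP is based on Amendment 3 and the protocol at hand is Amendment 5. The Amendment 5 change list mentions no diary scoring, but the text of Amendments 3 and 4 is not available to check.

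**Conclusion.** The point stands in this limited form. For PUCAI the SAP's day-selection rule differs from the protocol's in three ways: no preparation or endoscopy exclusion, no 10-day limit, and consecutive days preferred to the most recent eligible ones. The first can raise PUCAI and misclassify remission or response when an optional endoscopy took place about 0 to 4 days before the visit, assuming preparation the day before and a full diary. The number of subjects affected cannot be derived, since the documents give neither endoscopy timing nor diary completion. For Mayo and partial Mayo, the day-selection difference is confined to the consecutive-days wording, which matters only when an entry is missing.

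All analyses are descriptive, so no error rate or sample size is involved. What is at stake is the accuracy and reproducibility of reported proportions in about 55 subjects. That justifies a correction before database lock, but not a claim of known bias.

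**What to change.** Amend SAP section 6.0 as follows.

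- **PUCAI:** use the most recent two eligible days within 10 days before the visit, consecutive or not, excluding the bowel-preparation day, the endoscopy day and the two days after.
- **Mayo stool frequency and rectal bleeding:** use the most recent five eligible days within 14 days, consecutive or not, keeping the exclusions already there.
- **Other scoring rules, in the same edit:** score anti-diarrheal days 15 for the PUCAI stool-number item and 3 for Mayo stool frequency, and round the PUCAI total up to the next 5 points. The SAP's general convention against rounding during calculation then needs a stated exception.
- **If any departure is intended:** say so and give the reason.

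The cost is SAP wording and the matching derivation code. No new data, visits or procedures are needed.

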All time points and corresponding time windows are defined based on Rx days. The protocol specified visits and corresponding time windows are presented in the table below. Measures will only be displayed at the visits where they were planned to be measured. For example, Mayo score is collected at Weeks 0, 48, 96, 192 and 288/Premature Discontinuation (dependent on availability of optional endoscopy data at these timepoints).

Assigned Visit	Nominal Day	Time Window (Rx Day Range)
Week 0	1	≤ 1
Week 4	29	2 to 43
Week 8	57	44 to 71
Week 12	85	71 to 127
Week 24	169	128 to 211
Week 36	253	212 to 295
Week 48	337	296 to 379
Week 60	421	380 to 463
Week 72	505	464 to 547
Week 84	589	548 to 631
Week 96	673	632 to 715
Week 108	757	716 to 799
Week 120	841	800 to 925
Week 144	1009	926 to 1093
Week 168	1177	1094 to 1261
Week 192	1345	1262 to 1429
Week 216	1513	1430 to 1597
Week 240	1681	1598 to 1765
Week 264	1849	1766 to 1933
Week 288	2017	1934 to 2101

If more than one assessment is included in a time window the assessment closest to the nominal day should be used. If there were more than one observation with equal distance to the nominal day the latest one will be used in analyses. For any given variable, if more

than one measurement exists for a subject on the same day, the average of the measurements will be considered to be that subject's measurement for that day.

Missing Data Handling

In general, missing Baseline and safety data will not be imputed.

Baseline Value is Missing:

Subjects will be excluded from analysis of change from Baseline if Baseline evaluation is missing.

Missing Efficacy and Outcome Evaluations:

The following methods will be used for imputing missing values to perform the efficacy analyses.

[figure not shown]
For interim analyses, missing values will only be imputed up to the timepoint a patient could have potentially reached at the data cutoff for analyses.

Observed Cases (OC): missing values will not be used for the observed case analysis.

Last Observation Carried Forward (LOCF): For categorical and continuous efficacy variables the following rules will be used for LOCF approach:

- Baseline and pre-baseline values will not be used to impute the missing post-baseline values, and
- Missing values after baseline will be imputed using the last non-missing values after baseline and prior to the missing value.

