When calculating **IMPACT III** total score, if 4 or more of the items are missing then IMPACT III total score and all subscores will be considered missing. Otherwise, if there are 3 or fewer missing answers, the average of non-missing values will be used to replace the missing items for the total score and subscore calculation. If for subscores consisting of only 3 items (see 'Score Definitions' later in this Section), all of these items are missing and are replaced per above convention, a footnote will be added indicating for how many subjects the subscore included in the analysis has been fully imputed.

When calculating the **WPAI** scores, the following computational notes should be followed.

- Define Employment as a binary YES or NO variable where YES corresponds to "Employed" and NO corresponds to "Not Employed":
 - A subject will be considered EMPLOYED at a given visit if Q1 = YES or Q2 > 0 or Q4 > 0.
 - A subject will be considered UNEMPLOYED at a given visit if Q1 = NO and no positive hours recorded under Q2 and Q4 (i.e., if Q1 = NO AND $Q2 \le 0$ AND $Q4 \le 0$, then UNEMPLOYED).
 - Employment status for a subject will be considered missing at a given visit if Q1 = missing and no positive hours recorded under Q2 and Q4.
- If a subject is UNEMPLOYED or employment status is missing, then S1, S2, and S3 will be set to missing.
- If Q2 = 0 and Q4 = 0 or missing then Q2/(Q2 + Q4) = missing (i.e., S1 = missing).
- If Q2 = 0 and Q4 = 0, then set S3 to missing.
- If Q2 is missing or Q4 is missing, then set S1 and S3 to missing.
- If Q4 = missing, then DO NOT set Q5 = missing.
- If Q5 is missing, then apply the following rules:
 - \circ If Q2 > 0, Q4 = 0, and Q5 = missing, then S3 = 100%.
 - \circ If Q2 = 0, Q4 > 0, and Q5 = missing, then S3 is missing.
 - \circ If Q2 > 0, Q4 > 0, and Q5 = missing, then S3 is missing.
- Determine if a subject missed work (based on Q2) in order to analyze the proportion of subjects who missed work:
 - Create a binary (YES or NO) "missed work" variable.
 - A subject will be considered as yes to missed work if Q2 is greater than 0.
 - If Q2 = missing, then MISSED WORK = missing.
 - \circ If Q2 > 0, then MISSED WORK = YES
 - \circ If Q2 = 0, then MISSED WORK = NO

• Therefore, the proportion of subjects who missed work will be counted based on the number of subjects with MISSED WORK = YES.

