3. IMPACT III

The IMPACT III questionnaire assesses quality of life in IBD related fields and comprises 35 closed questions with a 5-point Likert scale for all answers ('good'

through 'bad' answers scored by 5 through 1; range of total score 35 - 175, higher scores suggesting higher quality of life).

Total Score: sum of Q1 - Q35

Subscores:

• Bowel symptoms (7 items: Q1, Q3, Q10, Q19, Q21, Q25, Q31)

• Systemic symptoms (3 items: Q6, Q28, Q32)

• Emotional functioning (7 items: Q4, Q5, Q11, Q12, Q13, Q16, Q29)

Social functioning (12 items: Q8, Q9, Q14, Q17, Q18, Q20, Q23, Q26, Q27, Q30, Q34, Q35)

• Body image (3 items: Q7, Q15, Q33)

• Treatment/interventions (3 items: Q2, Q22, Q24)

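### An IMPACT III subscore for a 3-item domain with no answers is built entirely from the other domains, yet stays in the efficacy summaries with only a footnoted count

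*SAP*

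**What the plan says.** The scoring rule is in SAP Section 6.0, under the heading on missing questionnaire items. It has three parts.

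- An upper limit: "if 4 or more of the items are missing then IMPACT III total score and all subscores will be considered missing".
- A fill-in below that limit: "the average of non-missing values will be used to replace the missing items for the total score and subscore calculation".
- A provision for a 3-item subscore in which "all of these items are missing and are replaced per above convention". In that case "a footnote will be added indicating for how many subjects the subscore included in the analysis has been fully imputed". The subscore is therefore kept.

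The score definitions in the same section describe "35 closed questions with a 5-point Likert scale for all answers", scored 1 to 5, and six domains: bowel symptoms (7 items), systemic symptoms (3), emotional functioning (7), social functioning (12), body image (3) and treatment/interventions (3).

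SAP Section 10.2 lists change from Baseline in the IMPACT III total and subscores among the efficacy endpoints. Section 10.1 reports continuous endpoints as changes from Baseline with 95% confidence intervals, on observed cases and with last observation carried forward. Section 10.4 names no specific sensitivity analysis.

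**The concern.** A domain subscore is reported separately from the total because it should describe that domain. Under this rule a child who answers none of the three body-image questions still receives a body-image score, taken from the bowel, systemic, emotional, social and treatment answers. That value enters the mean, the standard deviation and the confidence interval for body image. The footnote tells the reader how many such values there are but leaves them in the estimate.

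There is a second gap. When a 3-item domain is partly answered, the SAP does not say whether the average is taken over the whole questionnaire or over the domain. Two programmers could derive different subscores from the same form. The footnote covers only fully imputed subscores, so a partly filled one would not be flagged.

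**Working it through.** **Inputs.** From SAP Section 6.0: 35 items scored 1 to 5, the domain sizes above, and a limit of 3 missing items. From SAP Section 4.3: about 55 subjects expected outside Japan. This is an upper bound for IMPACT III, which is analysed only in those aged at least 9 years at Baseline. Assumption: a subscore is the sum of its items. The SAP states the sum only for the total.

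**Reproducing the SAP's own figure.** The domain sizes add to 7 + 3 + 7 + 12 + 3 + 3 = 35, and the item lists cover items 1 to 35 once each. The total runs from 35 × 1 = 35 to 35 × 5 = 175, as stated. A 3-item subscore runs from 3 to 15, a range of 12.

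**Which domains can be empty.** With at most 3 items missing, only the three 3-item domains can be. An empty one uses the whole allowance, so the 35 − 3 = 32 remaining answers all lie in other domains. No reading of the averaging rule avoids this.

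**Error for an empty domain.** Error = 3 × (mean of the other 32 answers − true domain mean).

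- Extremes: 3 × (5 − 1) = +12 and 3 × (1 − 5) = −12.
- Illustration with assumed values, other items 4 and true domain items 2: imputed 3 × 4 = 12, true 3 × 2 = 6, error 6, which is 6/12 = 50% of the range.

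**Partly answered domain, same values, if the average is over the questionnaire.**

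| Items missing of 3 | Fill-in value | Subscore | Error | Share of range | Footnote applies |
|---|---|---|---|---|---|
| 1 | (32 × 4 + 2 × 2)/34 = 3.88 | 2 + 2 + 3.88 = 7.88 | 1.88 | 15.7% | No |
| 2 | (32 × 4 + 2)/33 = 3.94 | 2 + 2 × 3.94 = 9.88 | 3.88 | 32.3% | No |
| 3 | 128/32 = 4.00 | 12 | 6 | 50% | Yes |

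If the average is over the domain, the first two rows give 6 and no error, because the assumed items are all 2.

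**Effect of one such child on a group mean.** Error divided by n.

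| n | Illustration (error 6) | Maximum (error 12) |
|---|---|---|
| 55 | 0.11 | 0.22 |
| 20 | 0.30 | 0.60 |
| 10 | 0.60 | 1.20 |

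**How specific the pattern is.** There are 35 × 34 × 33/6 = 6,545 ways to miss exactly three items, and 3 of them empty a domain (0.05%). This counts patterns. It is not a probability, because skipped items may cluster.

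**The case against.** The strongest defence is that the SAP foresaw the case and discloses it, that the pattern needs a specific set of three blanks, and that little depends on the result. Much of this stands. No confirmatory testing is done (SAP Sections 10.1 and 10.3). Protocol Section 5.3.2 places IMPACT III among the other measures of disease activity and names no subscores. Protocol Section 10.2 has site staff verify completion of the paper questionnaires, which should limit blanks. None of this gives the borrowed value any content about its domain, and disclosing a count does not take the value out of the mean.

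A reader might infer three stronger points that the documents do not support.

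- *That borrowed subscores are passed off as observed.* The SAP calls them fully imputed and requires their number to be shown.
- *That the rule contradicts the observed-case definition*, under which "missing values will not be used for the observed case analysis". That definition concerns evaluations missing at a visit. Item handling has its own heading and determines when a score exists at all. The SAP does not spell out the link, but this is not a clear contradiction.
- *That the scores are biased upward because sensitive items are skipped more often.* The documents give no item wording, item-missing rates or domain scores. The error can go either way.

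**Conclusion.** The point holds for an empty 3-item domain: the stated rule yields a subscore with no information on its own domain and keeps it in a listed efficacy endpoint. For a partly answered domain the finding is an ambiguity. It becomes an error only if the average is taken over the questionnaire.

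For one child the error can be large, up to 12 points either way on a 3 to 15 scale if subscores are item sums. For a group it is likely to be small: the illustrative child moves the mean by 0.11 points at n = 55 and 0.3 at n = 20. The example values are assumed, and neither the item-missing rate nor the direction of any bias can be known from the documents. The endpoint is descriptive. The change is worth making because it is cheap, but no main conclusion of the study depends on it.

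**What to change.** Amend the IMPACT III paragraph of SAP Section 6.0 as follows.

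- Keep the rule that 4 or more missing items sets the total and all subscores to missing. Applying that limit only to the total would allow more subscore imputation than the SAP does now.
- Keep the current fill-in for the total, and state that it uses the average over the whole questionnaire.
- For subscores, replace a missing item by the mean of that subject's answered items in the same domain.
- Set a 3-item subscore to missing at that visit when fewer than 2 of its 3 items are answered, or at minimum when none is. The larger domains need no threshold: with at most 3 items missing, at least 4 of 7 or 9 of 12 are answered.
- Delete the footnote on fully imputed subscores, which then has no use.

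The cost is a few sentences and minor programming. A few subject-visits lose a subscore that was not adequately measured, while their total is unaffected. Where items were filled in, the subscores may no longer add exactly to the total. In the one-item example the filled item is 3.88 in the total and 2 in the subscore, a difference of 1.88. A table note should say so.
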